5.6.4 Selection of Doses in the Study

Subject dosing is determined individually. Prior to subject enrollment, all anti-PD medications have been optimized and stabilized during the Screening Period. For subjects randomized to LCIG, the starting dose of the infusion after placement of the NJ and/or PEG-J tube will be based on the daily dose of the oral levodopa prior to or at the time of study entry. Subject dosing will be individually optimized.

The total dose/day of LCIG is composed of three individually adjusted doses: (i) the morning dose, (ii) the continuous maintenance dose and (iii) extra doses. The needs of individual subjects may vary depending on their particular condition and calculation of necessary dosing will be individualized based. The LCIG infusion is expected to infuse over approximately 16 hours each day with a rate of infusion within the range of 1 to 10 mL/hour (20 to 200 mg of levodopa/hour) in most instances. The maximum LCIG dose administered in this study should not exceed 200 mg of levodopa/hour for 26 weeks.

6.0 Complaints

A Complaint is any written, electronic, or oral communication that alleges deficiencies related to the physical characteristics, identity, quality, purity, potency, durability, reliability, safety, effectiveness, or performance of a product/device after it is released for distribution.

The investigational product in this trial contains both:

- An active pharmacological agent
- Device component(s) (cassette, tubing, pump, connectors, etc.).

Complaints associated with any component of this investigational product must be reported to the Sponsor (Section 6.2.2). For adverse events, please refer to Sections 6.1 through 6.1.6. For product complaints, please refer to Section 6.2.

6.1 Medical Complaints

The investigator will monitor each subject for clinical and laboratory evidence of adverse events on a routine basis throughout the study. The investigator will assess and record any adverse event in detail including the date of onset, event diagnosis (if known) or sign/symptom, severity, time course (end date, ongoing, intermittent), relationship of the adverse event to study drug, and any action(s) taken. For serious adverse events considered as having "no reasonable possibility" of being associated with study drug or the study device components, the investigator will provide an Other cause of the event. For adverse events to be considered intermittent, the events must be of similar nature and severity. Adverse events, whether in response to a query, observed by site personnel, or reported spontaneously by the subject will be recorded.

All adverse events will be followed to a satisfactory conclusion.

6.1.1 Definitions

6.1.1.1 Adverse Event

An adverse event (AE) is defined as any untoward medical occurrence in a patient or clinical investigation subject administered a pharmaceutical product and which does not necessarily have a causal relationship with this treatment. An adverse event can therefore be any unfavorable and unintended sign (including an abnormal laboratory finding), symptom, or disease temporally associated with the use of a medicinal (investigational) product, whether or not the event is considered causally related to the use of the product.

Such an event can result from use of the drug as stipulated in the protocol or labeling, as well as from accidental or intentional overdose, drug abuse, or drug withdrawal. Any worsening of a pre-existing condition or illness is considered an adverse event.

Worsening in severity of a reported adverse event should be reported as a new adverse event. Laboratory abnormalities and changes in vital signs are considered to be adverse events only if they result in discontinuation from the study, necessitate therapeutic medical intervention, and/or if the Investigator considers them to be adverse events.

An elective surgery/procedure scheduled to occur during a study will not be considered an adverse event if the surgery/procedure is being performed for a pre-existing condition and the surgery/procedure has been pre planned prior to study entry. However, if the pre-existing condition deteriorates unexpectedly during the study (e.g., surgery performed earlier than planned), then the deterioration of the condition for which the elective surgery/procedure is being done will be considered an adverse event. Also, fluctuating PD symptoms during titration should not be considered an adverse event.

6.1.1.2 Serious Adverse Events

If an adverse event meets any of the following criteria, it is to be reported to AbbVie as a serious adverse event (SAE) within 24 hours of the site being made aware of the serious adverse event.

A hospitalization prior to the first screening visit (SV1), allowing the subject to arrive at the clinic in the "Off" state, will not be regarded as an SAE. If not associated with worsening of Parkinson's disease symptoms, a hospitalization for dose adjustments of LCIG will not be regarded as a SAE. A hospitalization because of a Product Complaint, such as a device dislocation without AE (i.e., without health impairment) will not be regarded as an SAE.

Hospitalization for scheduled tube placement/replacement should not be considered an SAE.

Death of Subject	An event that results in the death of a subject.
Life-Threatening	An event that, in the opinion of the investigator, would have resulted in immediate fatality if medical intervention had not been taken. This does not include an event that would have been fatal if it had occurred in a more severe form.
Hospitalization or Prolongation of Hospitalization	An event that results in an admission to the hospital for any length of time or prolongs the subject's hospital stay. This does not include an emergency room visit or admission to an outpatient facility.
Congenital Anomaly	An anomaly detected at or after birth, or any anomaly that results in fetal loss.
Persistent or Significant Disability/Incapacity	An event that results in a condition that substantially interferes with the activities of daily living of a study subject. Disability is not intended to include experiences of relatively minor medical significance such as headache, nausea, vomiting, diarrhea, influenza, and accidental trauma (e.g., sprained ankle).
Important Medical Event Requiring Medical or Surgical Intervention to Prevent Serious Outcome	An important medical event that may not be immediately life-threatening or result in death or hospitalization, but based on medical judgment may jeopardize the subject and may require medical or surgical intervention to prevent any of the outcomes listed above (i.e., death of subject, life-threatening, hospitalization, prolongation of hospitalization, congenital anomaly, or persistent or significant disability/incapacity). Additionally, any elective or spontaneous abortion or stillbirth is considered an important medical event. Examples of such events include allergic bronchospasm requiring intensive treatment in an emergency room or at home, blood dyscrasias or convulsions that do not result in inpatient hospitalization, or the development of drug dependency or drug abuse.

For serious adverse events with the outcome of death, the date and cause of death will be recorded on the appropriate case report form.

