In the previous Phase 3 clinical program, as observed in an integrated summary of safety, AEs were common and occurred in 93.9% of the 412 subjects in the Open-Label LCIG Analysis Set (Phase 3 Studies S187.3.003, S187.3.004, and S187.3.005). The most common treatment emergent adverse events (TEAEs) were complication of device insertion (33.3%), abdominal pain (28.2%), postoperative wound infection (23.5%), insomnia (23.3%), fall (23.1%), procedural pain (20.9%), excessive granulation tissue (20.6%), nausea (20.4%), constipation (20.4%), and incision site erythema (20.1%) (Table 1). These AEs are commonly associated with underlying PD or are frequently observed following PEG-J placement. Treatment emergent adverse events reported in $\geq 10\%$ of subjects by descending frequency in a pooled open-label analysis set

representing a mean treatment duration of 854 days (open-label LCIG analysis set) are in Table 1.

Table 1. TEAEs Reported in $\geq 10\%$ of Subjects by Descending Frequency (Open-Label LCIG Analysis Set)

Preferred Term	N = 412 Number (%) of Subjects
Any adverse event	387 (93.9)
Complication of device insertion	137 (33.3)
Abdominal pain	116 (28.2)
Postoperative wound infection	97 (23.5)
Insomnia	96 (23.3)
Fall	95 (23.1)
Procedural pain	86 (20.9)
Excessive granulation tissue	85 (20.6)
Nausea	84 (20.4)
Constipation	84 (20.4)
Incision site erythema	83 (20.1)
Urinary tract infection	71 (17.2)
Vitamin B ₆ decreased	65 (15.8)
Anxiety	61 (14.8)
Procedural site reaction	61 (14.8)
Dyskinesia	60 (14.6)
Parkinson's disease	59 (14.3)
Weight decreased	59 (14.3)
Depression	55 (13.3)
Blood homocysteine increased	56 (13.6)
Back pain	46 (11.2)
Post procedural discharge	45 (10.9)
Orthostatic hypotension	44 (10.7)
Vomiting	43 (10.4)
Diarrhoea	43 (10.4)
Headache	41 (10.0)

SAEs occurred in 47.1% of the 412 subjects in a pooled Open-Label LCIG Analysis Set (Phase 3 Studies S187.3.003, S187.3.004, and S187.3.005). SAEs that occurred in $\geq 2\%$ of subjects were as follows: Complications of device insertion (7.8%), pneumonia (4.9%), abdominal pain (4.1%), hip fracture (2.4%), Parkinson's disease (2.4%), peritonitis (2.4%), weight decreased (2.4%), fall (2.4%), polyneuropathy (2.2%) and device dislocation (2.2%). These data are on file at AbbVie.

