6.2 Product Complaint

6.2.1 Definition

A Product Complaint is any Complaint (see Section 6.0 for the definition) related to the biologic or drug component of the product or to the medical device component(s).

For a product this may include, but is not limited to, damaged/broken product or packaging, product appearance whose color/markings do not match the labeling, labeling discrepancies/inadequacies in the labeling/instructions (example: printing illegible), missing components/product, device not working properly, or packaging issues.

For medical devices, a product complaint also includes all deaths of a patient using the device, any illness, injury, or adverse event in the proximity of the device, an adverse

event that could be a result of using the device, any event needing medical or surgical intervention including hospitalization while using the device and use errors.

Any information available to help in the determination of causality by the device to the events outlined directly above should be captured.

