10.2.2 Adverse Event Incidence

The number and percentage of subjects experiencing one or more adverse events in the following adverse event categories during the 26-week Treatment Period will be summarized for each treatment group and for overall subjects by primary SOC and PT.

- Any TEAE
- Any serious TEAE
- Any TEAE that led to discontinuation of study drug

The percentage of subjects in the LCIG group and in the OMT group will be compared using Fisher's exact test. Only P values ≤ 0.100 when rounded to three digits will be presented.

The number and percentage of subjects experiencing one or more adverse events in the following adverse event categories during the Extension/Transition Period will be summarized for OMT/LCIG subjects who enter the Extension/Transition Period by primary SOC and PT.

- Any TEAE
- Any serious TEAE
- Any TEAE that led to discontinuation of study drug

The number and percentage of subjects experiencing one or more TEAEs during the 26-week Treatment Period will also be summarized for each treatment group and for overall subjects by maximum severity category (mild, moderate, severe, or unknown) and primary SOC and PT. Subjects reporting more than one TEAE for a given PT will be counted only once for that term in the most severe category reported. If a subject has an adverse event with unknown severity, then the subject will be counted in the severity category of "unknown," even if the subject has another occurrence of the same event with a severity present. The only exception is if the subject has another occurrence of the same

adverse event with the most extreme severity – "Severe." In this case, the subject will be counted under the "Severe" category.

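### The SAE exemption for LCIG dose-adjustment admissions does not require that no adverse event is present and has no OMT counterpart, so the by-arm comparison of serious events can undercount LCIG

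*Protocol*

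**What the plan says.** Protocol Section 6.1.1.2 makes an adverse event the precondition for any serious event, in both arms: "If an adverse event meets any of the following criteria, it is to be reported to AbbVie as a serious adverse event (SAE". It then lists exemptions. Two matter here.

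- Dose adjustment: on the one condition that there is no link to worsening Parkinson's symptoms, "a hospitalization for dose adjustments of LCIG will not be regarded as a SAE".
- Device: "A hospitalization because of a Product Complaint, such as a device dislocation without AE", explained as one that does no harm to health, is likewise not an SAE.

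The section also exempts scheduled tube placement and replacement. No sentence covers admission to adjust OMT, although Section 5.1.2.1 allows OMT changes when medically justified.

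Three other places bear on how these exemptions read:

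- Section 6.2.1 defines a medical-device Product Complaint to include adverse events close to the device and "any event needing medical or surgical intervention including hospitalization while using the device and use errors".
- Section 6.1.1.1 states that fluctuating Parkinson's symptoms during titration are not adverse events.
- Section 5.1.2.2 says that after Day 28 the LCIG dose is to stay stable unless a change is needed for safety.

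On analysis, SAP 10.2.2 tabulates serious treatment-emergent events by system organ class and preferred term and adds: "The percentage of subjects in the LCIG group and in the OMT group will be compared using Fisher's exact test". Only P values of 0.100 or less are printed.

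**The concern.** Safety relative to OMT is a stated secondary objective (Protocol Section 4.0), and the trial is open-label. The site that classifies each admission knows the arm. A rule that switches off the hospitalization criterion for one arm only, on conditions looser than the absence of an adverse event, can move events out of the serious category on one side of the comparison.

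Nothing else in the plan would show that this had happened. Section 6.2.2 says that complaints associated with adverse events go into the study summary and that the rest are monitored. The synopsis lists device-related product complaints among the safety summaries, but SAP Section 10 contains no such summary, although SAP Section 12.0 declares no change in analysis from the protocol. SAP 8.8 counts tube replacements, not admissions. Exempt admissions therefore appear in no planned table.

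**Working it through.** **Step 1. Set the rules side by side by type of admission.** This uses Protocol 6.1.1.1, 6.1.1.2 and 6.2.1, read literally.

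| Reason for admission | LCIG | OMT | Same rule? |
|---|---|---|---|
| Dose adjustment, no adverse event | Not an SAE | Not an SAE, because no adverse event | Yes |
| Dose adjustment with Parkinson's worsening | Exemption does not apply | Hospitalization criterion applies | Yes, except during titration (Step 3) |
| Dose adjustment because of another adverse event | Exempt | Hospitalization criterion applies | **No** |
| Device problem, no adverse event | Not an SAE | Does not arise | No SAE lost |
| Device complaint that is, or comes with, an adverse event | Unclear | Does not arise | **Unclear** |

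The third row is the gap. The dose-adjustment sentence has one condition, the absence of Parkinson's worsening. The device sentence next to it mentions the absence of an adverse event; the dose-adjustment sentence does not.

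The last row is unclear because the condition sits inside an example: "such as a device dislocation without AE (i.e., without health impairment) will not be regarded as an SAE". It does not clearly govern the whole class of Product Complaint admissions, and Section 6.2.1 puts adverse events and hospitalizations into that class.

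**Step 2. Ask whether the third row can occur.** Section 5.1.2.2 reserves LCIG dose changes after Day 28 for safety reasons, so a later admission for dose adjustment is likely to have an adverse event behind it. Section 5.5.4 is looser and allows adjustment throughout the study as clinically indicated. The two statements need to be reconciled, but the third row can arise under either.

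**Step 3. Check the worsening condition.** Section 6.1.1.1 takes fluctuating Parkinson's symptoms during titration out of adverse-event status, and only LCIG is titrated. The protocol does not say how such fluctuation is told apart from the worsening that defeats the exemption in 6.1.1.2.

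**Step 4. Illustrate sensitivity.** The documents state no expected SAE rate by arm and no number of exempt admissions, so there is no plan figure to reproduce. The inputs are 88 subjects randomized 1:1 (Protocol 8.2), hence 44 per arm, and a two-sided test at 0.050 (SAP 10.1). The SAE counts are assumed. With *s* subjects having an SAE in total, the probability of *x* of them in the LCIG arm is C(44, x) · C(44, s − x) / C(88, s). The two-sided P sums this over all tables no more probable than the one observed.

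| OMT | LCIG | Difference | Fisher P |
|---|---|---|---|
| 6/44 | 15/44 | 9/44 = 20.5 points | 0.044 |
| 6/44 | 12/44 (three exempt) | 6/44 = 13.6 points | 0.19 |
| 6/44 | 11/44 (four exempt) | 5/44 = 11.4 points | 0.28 |

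Each reclassified subject moves the difference by 1/44 = 2.3 points. Under the 0.100 printing rule, the second and third rows would show no P value.

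Other assumed counts show when this matters:

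- OMT 4, LCIG 10: P = 0.143. Adding back 1, 2 or 3 LCIG subjects gives 0.087, 0.051 and 0.029.
- OMT 4, LCIG 4: still 0.352 after adding back four.
- OMT 4, LCIG 14: already 0.016 with none added.

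Only borderline results are sensitive.

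**Step 5. Look for a scale.** The earlier Phase 3 pool in Section 3.2 had device dislocation as an SAE in 2.2% of 412 subjects, over a mean of 854 days. At that rate 0.022 × 44 = 0.97, about one subject. If scaled in proportion to 26 weeks (an assumption), it is 0.97 × 182/854 ≈ 0.2. These were events classed as serious, so they do not estimate the number that would be exempt here.

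**The case against.** The strongest reply is that an SAE must first be an adverse event in either arm, so an exemption for admissions without one removes nothing. That is right for device admissions that truly involve no adverse event, and for dose adjustment without one. A reader might infer that every admission for device failure is lost, or that every OMT dose-adjustment admission counts. The documents support neither. The reply does not reach the dose-adjustment sentence, which never mentions adverse events, or the part of the device class outside the example.

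Second, many LCIG stays are planned. Section 5.1.2.2 lets subjects remain in hospital while the dose is optimized, and counting those stays as SAEs would inflate the LCIG arm. This stands, and it is why such stays should be shown separately.

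Third, admissions for Parkinson's deterioration, the ones most like what an OMT subject would have, are not exempt. This also stands, subject to the titration carve-out.

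Fourth, the exemption removes only the hospitalization route to seriousness. The adverse event is still recorded and can be serious on another criterion. GI and procedure-related events are tabulated by arm (SAP 10.2.3), and Product Complaints are reported within 24 hours (Protocol 6.2.2). The Fisher tests carry no multiplicity control and no success criterion. All of this limits the consequence, but none of it shows how many admissions were exempted.

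Finally, a reader might infer that SAE rates here are not comparable with the earlier pool. Section 3.2 gives that pool's rates but not its SAE definition, and a dislocation that harms the subject can still be an SAE in this trial. Nor does that pool's 7.8% for complication of device insertion measure the effect, since it is an adverse-event term already classed as serious there, not a count of exempt admissions.

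**Conclusion.** The point holds as a gap in the definition. Read literally, Section 6.1.1.2 lets an LCIG admission driven by an adverse event escape serious status where the same OMT admission would not, and the device exemption is not clearly confined to cases without an adverse event. The serious-event comparison can therefore undercount LCIG.

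It is tempting to say that it does undercount LCIG. The documents do not show that: they give no number of exempt admissions, and sites may read the exemptions narrowly. The P values above rest on assumed counts and on 44 analysed subjects per arm. They show that three or four reclassified subjects could change a borderline result, and that results away from the border would not change. The correction is cheap, and it removes a one-sided rule from an open-label safety comparison, so it should be made.

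**What to change.** 1. In Protocol 6.1.1.2, limit the dose-adjustment exemption to admissions without an adverse event, and word it for adjustment of randomized treatment in either arm. Make the no-adverse-event condition govern the whole Product Complaint exemption, not just the example. Reconcile the worsening condition with the statement on titration symptoms in 6.1.1.1.
2. Record the reason for every inpatient admission after randomization, in both arms.
3. In SAP 10.2, add a table of unplanned admissions by arm, with the risk difference and its 95% confidence interval. Show exempt admissions and planned placement or titration stays on separate lines, not as SAEs.

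The cost is a wording change, one eCRF field and one safety table. The downside for the sponsor is a possibly less favourable LCIG admission rate.

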6.1.1.3 Adverse Events of Special Interest

Adverse events of special interest (AESI) are:

- Gastrointestinal and gastrointestinal procedure related events
- Polyneuropathy
- Weight loss

For AESIs, serious and nonserious, meeting pre-defined criteria, specific questionnaires will be used to standardize the collection of follow-up information. The AESI questionnaires are either sent to the site after Sponsor review or issued within the Electronic Data Capture (EDC) system once applicable. The Investigator will email the completed questionnaires to the AbbVie Neuroscience Safety Management Team or enter the information into the EDC system once applicable. If a subject develops signs and symptoms of polyneuropathy a standard panel of examinations will be suggested to the Investigator and certain laboratory tests (specified in questionnaire) will be required by the Sponsor. The Investigator may perform additional other assessments that are deemed appropriate for further evaluation of polyneuropathy symptoms based on the presentation of the individual subject. If weight loss is considered to be clinically significant, preventative measures will be taken to counteract weight loss.

For all AESIs, if the event meets seriousness criteria, the Investigator will report the event to the Sponsor within 24 hours of the site being made aware of the event according to Section 6.1.5.

Neuroscience Clinical Safety Management Team
AbbVie
[REDACTED]
[name]
[name]

Telephone Contact Information:
Office: [REDACTED]
Fax: [REDACTED]
Email: [REDACTED]

6.1.2 Adverse Event Severity

The investigator will use the following definitions to rate the severity of each adverse event:

Mild	The adverse event is transient and easily tolerated by the subject.
Moderate	The adverse event causes the subject discomfort and interrupts the subject's usual activities.
Severe	The adverse event causes considerable interference with the subject's usual activities and may be incapacitating or life-threatening.

